## 9.0 Confidentiality, Privacy and Data Management

## 9.1 Confidentiality

#### 9.1.1 Identifiers associated with data and/or specimens

The identifiers that will be used to label the study data and/or specimens may include some or all of the following: age, date of birth, height, weight, body mass index, and the assigned subject ID. Samples that are sent to Quest Diagnostics for screening assays will contain the name. However, name and subject ID will not both be present on any data or specimens.

## 9.1.1.1 Use of Codes, Master List

The list linking the code numbers (subject ID) to the participant's name and contact information will be stored in a password-protected file on password-protected computers. This file will also be stored on a server that only lab personnel can access after they have logged into a password-protected computer using their personal HHD username and password. Access to this list will be limited to lab personnel. After all of the data for the study is entered and analyzed, manuscripts have been published, the study is completed, and it has been determined that the list is no longer needed for data analysis and publication reasons, the list will be destroyed.

## 9.1.2 Storage of Data and/or Specimens

Both hardcopy and electronic data will be stored in the Women's Health and Exercise Lab in Noll Laboratory. The hardcopy data will be stored in locked offices or labs of the Women's Health and Exercise Lab (Noll Lab Rooms 109,110,122,123,124,116,117,206, 207). Electronic data will be stored on password-protected computers in our laboratory. Only lab personnel can access the data after they log into the computer using their personal HHD username and password. Furthermore, privileges to view the research drives with the lab files is under the administration of the lab supervisors and the postdoctoral scholar. Therefore, only those given permission to view the research drives are able to do so after logging in to the computer.

Specimens will be stored in -20C or -80C freezers that are located in Noll Lab (Noll basement and hallway, Noll rooms 116,117,121,124).

Data and samples will be stored indefinitely until it is determined that they are no longer needed. The exception to this is if subjects did not provide permission for us to keep their samples indefinitely for future undetermined research. In this case, the samples will be destroyed when it has been determined that the samples are no longer needed for this research study (all data has been analyzed and manuscripts published).

The informed consent contains a section specific for sample donation for future research. If permission is granted to keep the samples for future research, participants will initial and sign the consent form in the correct spaces as shown below:

You should initial below to indicate what you want regarding the storage of your leftover blood for future research studies.

a. Your samples may be stored and used for future research studies to learn about metabolic- or endocrine-related conditions (conditions involving hormones).

\_Yes \_\_\_\_

b. Your samples may be shared with other investigators/groups without any identifying information. Yes No

## 9.1.3 Access to Data and/or Specimens

No

Only lab personnel who have completed the appropriate trainings will have access to the data or specimens.

## 9.1.4 Transferring Data and/or Specimens

Data and/or specimens may be transferred to the co-investigator, [name]. She is located in Boston, Massachusetts and is associated with the Neuroendocrine Unit of Massachusetts General Hospital and with Harvard Medical School. The transfer of specimens will occur according to guidelines established by Penn State Environmental Health and Safety (EHS) and will occur under the supervision of Penn State EHS. The transfer of data – either paper or electronic – will occur via postal service or e-mail; however, the names of subjects will not be attached to this data to ensure privacy and confidentiality.

## 9.2 Privacy

The study team that has been approved to work on the protocol will have access to hardcopy data, electronic data, subject contact information, and the list linking the subject name to the subject ID. Study team members will have access to the locked offices as well as their personal HHD login username and password. Access to the files stored on the research drive will be permitted at the discretion of those serving as administrators of the research drive (i.e. the lab supervisors and/or investigators of the study). Information will be stored in locked offices in our laboratory and on password-protected computers. We will never identify the participants' data in publications or presentations resulting from the research.

Interactions with the subjects and collection of personal information will be conducted in a professional manner by trained lab personnel in a laboratory space (office or testing room). The identity and personal information of subjects will be treated as confidential information and remain among the study group.

Only information that is pertinent to completing the study protocol will be asked of the participants. Research procedures will be explained in detail to subjects, and subjects will not be pressured, coerced, or forced to answer any questions or complete any procedures that they refuse to answer/complete. Subjects who did not wish to answer certain questions or complete certain procedures will be reminded that study participation is voluntary and can be stopped at any time.

## 10.0 Data and Safety Monitoring Plan

This study does not involve more than minimal risk to study participants.

- **10.1 Periodic evaluation of data** Not applicable
- **10.2 Data that are reviewed** Not applicable
- **10.3 Method of collection of safety information** Not applicable
- **10.4 Frequency of data collection** Not applicable
- **10.5** Individual's reviewing the data Not applicable
- **10.6 Frequency of review of cumulative data** Not applicable
- **10.7 Statistical tests** Not applicable
- **10.8 Suspension of research** Not applicable

## 11.0 Risks

COC Therapy (for COC group): There are several rare risks associated with using birth control pills including, but not limited to, blood clots, heart attack, stroke, bleeding in the brain, gall bladder disease, formation of liver tumors, breast cancer, high

blood pressure, vision problems, and unfavorable cholesterol levels. It is unlikely that a complication will occur because the risk of serious disease or death is very small in healthy women without underlying risk factors. Further, we are excluding women who have contraindications to COC therapy (i.e., smokers; women with a history of blood clots, heart disease, or stroke; women with hypertension, liver or gallbladder disease, cancer, or diabetes; women who have recently had major surgery with prolonged immobilization; women who are breastfeeding or recently postpartum). Additionally, symptoms such as nausea, vomiting, abdominal cramps and bloating, breakthrough bleeding, migraine headaches, breast tenderness, edema (swelling), melasma (spotty darkening of skin), yellowing of the skin, weight and appetite changes, rash, intolerance to contact lenses, depression and/or anxiety, loss of scalp hair, and vaginal infections may be associated with taking the birth control pills. In general, the most common complaint while taking birth control pills is breakthrough bleeding. Because this study is a short duration (6 weeks), this will resolve quickly after study completion.

TDC Therapy (for TDC group): Potential side effects of TDC use include nausea, breast discomfort, headache, skin irritation, breakthrough bleeding, edema, melasma (spotty darkening of skin), dizziness, and gastrointestinal problems. In the case of skin irritation, the patch may be removed and moved to a different location to reduce irritation. For other side effects, the subjects will be referred to a physician in the CRC or will be encouraged to contact their own health care provider. Serious risks associated with TDC therapy include blood clots, heart attack, stroke, and gallbladder disease. In rare cases, liver tumors or cancer of the reproductive organs/breasts may occur. However, these risks will be minimized by only including healthy women who do not present with contraindications for TDC therapy (for example: smokers; women with a history of blood clots, heart disease, or stroke; women with hypertension, liver or gallbladder disease, cancer, or diabetes; women who have recently had major surgery with prolonged immobilization; women who are breastfeeding or recently postpartum).

For a detailed list of the risks/side effects associated with TDC (Xulane), please consult the following website: http://dailymed.nlm.nih.gov/dailymed/drugInfo.cfm?setid=f7848550-086a-43d8-8ae5-047f4b9e4382

CVR Therapy (for CVR group): Potential common side effects of CVR include vaginitis, headaches, mood changes, devicerelated events (expulsion/discomfort/foreign body sensation), nausea and vomiting, vaginal discharge, increased body weight, vaginal discomfort, breast pain or tenderness, dysmenorrhea, abdominal pain, acne, decreased libido, and chloasma. Serious risks associated with CVR use are deep vein thrombosis, anxiety, cholelithiasis, vomiting, strokes and myocardial infarction, toxic shock syndrome, impaired liver function and liver tumors, increased blood pressure, and gallbladder disease. These risks will be minimized by only including healthy women who do not present with contraindications for hormonal contraceptive therapy.

Resting Blood Samples: The risks associated with single blood samples obtained with a needle and syringe or intravenous catheter may include one or all of the following: local discomfort, occasional dizziness and nausea, and black and blue marks. Blood clots attached to the walls of a blood vessel, and infections are very rare but are also potential risks. These risks will be minimized or eliminated by having only trained individuals who use sterile techniques draw blood. A trained assistant will closely monitor the subject while blood is being obtained in a supine position.

Subcutaneous GH administration: Growth hormone can sometimes cause side effects. The study participant may immediately experience pain, bleeding or swelling at the site of the injection. Other side effects may develop more slowly. Common side effects or most frequently observed adverse reactions include 1) swelling of the hands and feet, 2) carpal tunnel syndrome, 3) joint and back pain, 4) burning or tingling of the skin, 5) stuffy nose, 6) headaches, and 7) temporary high blood sugar (if the subject did not have high blood sugar when she started taking the study drug, then this condition should go away when the injections are stopped). Uncommon but potentially severe side effects include 1) high blood pressure, 2) pain and burning at the site of injection, 3) increased liver enzymes, 4) a dimple at the site of injection (this may happen if the study drug is always injected in the same place; to prevent this, the place where the injection is performed should be changed often), 5 previously present nevi (black birth marks) may increase in size (rare), 6) allergic reactions to a chemical called *m*-cresol, which is part of the study drug injection, 7) feeling tired or cold due to production of less thyroid hormone, resulting in puffy boggy swelling around the eyes, on the backs of the hands and feet, above the collarbone, 8) increase in pressure inside the brain causing severe headache (rarely occurs and should go away if the study drug dose is lowered or stopped), 9) diabetic retinopathy, 10) pancreatitis. Most of these symptoms disappear by themselves after a period of time or with a decrease in dosage or stopping of the drug. If symptoms do not go away, then the subject will need to stop taking the study drug. A higher risk for leukemia (a type of blood cancer) from growth hormone was noted in one small study. However experts now agree that the risk for

Page 26 of 37 (V. 12/5/2013)

leukemia in people receiving growth hormone is not greater than that for anybody else. Lastly, giving growth hormone in pregnancy can be harmful to the unborn baby; however, we will do a pregnancy test during baseline to ensure that the subject is not pregnant.

Overnight Fast: After the overnight fast, subjects may feel faint or dizzy. They are encouraged to drink water the morning of the blood draw and will be provided with a snack after all blood draws required for the study visit are completed.

Blood Loss: There may be a risk of reduced amount of blood (plasma volume), red blood cell count or the amount of ironcontaining substances that carry oxygen on red blood cells (hemoglobin levels) as a result of the blood lost over the course of the study. To minimize risks, we intend to screen individuals who may have low levels of hemoglobin and hematocrit. If these parameters are out of the normal range during the screening tests, these volunteers may be discontinued from the study or be required to wait several weeks prior to beginning the study after it has been determined that hemoglobin and hematocrit are in the normal range.

DXA Body Composition Assessment: The Dual Energy X-ray Absorptiometry (DXA) body composition procedure exposes an individual to a small amount of radiation where the X-ray beam crosses the body. This protocol calls for one total body scan. On occasion a scan may need to be repeated for quality control purposes. This radiation exposure is not necessary for medical care and is for research purposes only. There is minimal risk from this exposure. To ensure that a fetus is not exposed to radiation, a urinary pregnancy test will be conducted prior to the DXA scan.

Urine Sample for Pregnancy Tests: There are no known risks associated with the self-collection of one's urine. Volunteers will be given screw top and airtight containers to collect the urine.

Exercise Testing (VO2max): During exercise testing, volunteers may occasionally experience lightheadedness, chest discomfort, and cramping in the legs. Irregular heart beats and irregular blood pressure responses may occur. The risk of death during an exercise test is minor (0.5 per 10,000 tests), but does exist. These risks are usually found in individuals with existing heart conditions. Other potential risks, including fainting, nausea, muscle strain, and muscle soreness, will be minimized by proper warm-up procedures. Proper procedures for stopping the tests will be observed should a participant have abnormal symptoms associated with this test. Should an emergency situation occur, research personnel will call 911. During the exercise test, heart rate will be monitored continuously via a Polar heart rate monitor and rating of perceived exertion (RPE); blood pressure will be monitored before and after the test. Expired air will be collected using standard equipment in order to assess maximal oxygen uptake, which is a marker of aerobic fitness. A medical history will be obtained in order to identify absolute and relative contraindications to exercise testing. Trained personnel will administer the exercise tests and follow the proper procedures according to the guidelines of the American College of Sports Medicine (ACSM).

Physical Activity Assessments: There are no known risks associated with the collection of information about one's exercise practices.

Additional Costs Associated with Participation in Study: Study participants may spend additional money (that is not included in the compensation) on transportation to and from the laboratory.

Inconveniences: The following aspects of the study may represent inconveniences: frequent lab visits, fasting prior to and during blood sampling, repeated blood sampling, long study visits, two 4-day periods of subcutaneous injections, pregnancy tests, daily food logs, daily activity logs, daily menstrual logs, questionnaires, tests which are physically invasive and involve wearing cumbersome equipment.

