## 3.2 Exclusion Criteria

- 1) Non-weight bearing exercise as primary mode of physical activity
- 2) Known or suspected metabolic or endocrine disease
- 3) Pregnant
- 4) Currently consuming large amounts of soy products
- 5) Regular consumption of grapefruit juice
- 6) Current clinical eating disorder or other axis 1 psychiatric or bipolar disorders
- 7) Oral or hormonal contraceptive use in the last 6 months
- 8) Currently amenorrheic
- 9) Hyperparathyroidism
- 10)Liver or renal disease
- 11)Evidence of malabsorption or skeletal disorder
- 12)Thyroid abnormalities (controlled hypothyroidism acceptable)
- 13) Chronic use of non-steroidal anti-inflammatory drugs (NSAIDS)
- 14) Taking medications known to have interactions with contraceptive therapy (see section 6.4.6.5)
- 15) Division I Athlete, on or off season
- 16)Other Exclusion Criteria proposed by the World Health Organization COC Contraindications (Grossman, 2011) For this list of exclusion criteria, please see "WHO Criteria for Contraindication to COC Use" in the Supporting Documents section.

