## 3.3 Early Withdrawal of Subjects

#### 3.3.1 Criteria for removal from study

Subjects will be removed from the study for the following reasons:

- 1) Failure of subject to adhere to protocol requirements
- 2) Subject is no longer interested in participating and decides to withdraw
- 3) Subject becomes pregnant during the study
- 4) Identification of a disease or underlying health condition that precludes participation in the study
- 5) Subject becomes unwilling to adhere to maintenance of current exercise training and diet
- 6) Subject does not respond well to contraceptive therapy or GH administration, potentially compromising her health

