**NuvaRing Packaging:** NuvaRing (etonogestrel/ethinyl estradiol vaginal ring) is a nonbiodegradable, flexible, transparent, colorless to almost colorless, combination contraceptive vaginal ring containing two active components, a progestin, etonogestrel (13-ethyl-17-hydroxy-11-methylene-18,19-dinor-17 $\alpha$ -pregn-4-en-20-yn-3-one) and an estrogen, ethinyl estradiol (19-nor-17 $\alpha$ -pregna-1,3,5(10)-trien-20-yne-3,17-diol). When placed in the vagina, each ring releases on average 0.120 mg/day of etonogestrel and 0.015 mg/day of ethinyl estradiol over a three-week period of use. NuvaRing is made of ethylene vinylacetate copolymers (28% and 9% vinylacetate) and magnesium stearate and contains 11.7 mg etonogestrel and 2.7 mg ethinyl estradiol. NuvaRing is not made with natural rubber latex. NuvaRing has an outer diameter of 54 mm and a cross-sectional diameter of 4 mm. The molecular weights for etonogestrel and ethinyl estradiol are 324.46 and 296.40, respectively.

For the purposes of this study, each subject will receive three rings. The subjects will be instructed to insert the first ring during the first 24 hours of her menstrual period (day 1) at the start of the intervention. The ring will be in place continuously for 3 weeks and will be removed on day 22, after 21 days of continuous use. Day 22-28 will be a ring-free week. A second ring will be used for days 29-49 (removed on day 50 after 21 days of continuous use), and a third ring will be used for the remainder of the study (day 50 until the end of post-study period).

**Recombinant Human GH (rhGH, Omnitrope)** will be purchased from a pharmacy. It is a somatropin (rDNA origin) injection. We will be using 5.8 mg vials of Omnitrope. The vials contain a lypholized powder which is reconstituted with bacteriostatic water (contains benzyl alcohol as a preservative).

The lypholized powder will be reconstituted with the bacteriostatic water by nurses in the CRC. The Omnitrope vial with the diluent can be stored for 3 weeks. For each subject and for each injection, the nurses will draw up into a syringe the exact amount that is needed for that subject on that day. The exact dose to be injected each day depends on the subject's body weight, which will be supplied to the CRC.

Page 20 of 37 (V. 12/5/2013)

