#### 6.4.6.2 Storage

All study drugs will be stored in the Clinical Research Center following the storage requirements by the manufacturer.

Apri oral pills and Xulane transdermal patches will be stored at room temperature (25 degrees Celsius) in a locked cabinet in the CRC. Unused transdermal patches will be kept in their protective pouches. The subjects will be instructed to fold the sticky sides of the used patch together and put back in the protective pouch to be returned to the study group.

The pouches containing the NuvaRing will be stored in a research-designated, locked refrigerator (2-8 degrees Celsius) in the CRC. After being dispensed to the subjects, the NuvaRing can be stored at room temperature (25 degrees Celsius). The subjects will be instructed to keep the pouch with the ring out of direct sunlight and temperatures exceeding 30 degrees Celsius.

The rhGH (Omnitrope) will be stored protected from light in a research-designated locked refrigerator in the CRC at a temperature of 2 to 8 degrees Celsius. This locked refrigerator is only used for study drugs and the temperature is monitored daily. The powder form will be stored until the expiration date, and the reconstituted form that is used for injection will be stored for 3 weeks then discarded.

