#### 6.4.6.3 Preparation and Dispensing

The pharmaceuticals in this study (contraceptive therapy and growth hormone) will be prescribed by [name] or a CRC physician ([name]), who are both members of the study team for this research.

Study drug will be assigned to each subject indicating preference for contraceptive therapy by a block of 3 random assignment to oral, transdermal, or vaginal therapy. Each subject will be supplied with three oral pill packets, seven or eight transdermal patches (more will be provided as necessary if a patch falls off during the week), or three vaginal ring pouches. Once assigned to the study group, a CRC nursing staff member and a research WHEL staff member will dispense the study drug to the subject and provide detailed instructions regarding how to take the study drug.

For the rhGH, nurses in the CRC will reconstitute the Omnitrope vial of powder using a vial of diluent (bacteriostatic water with benzyl alcohol). The appropriate dose for each subject will be calculated by CRC and WHEL study staff (0.033 mg/kg/d). Uploaded on the CATS system is a detailed instruction sheet from the manufacturer on how to prepare and administer the drug. The injections will be given by the CRC nursing staff.

In addition to detailed instructions from the study team, subjects will receive the patient information for each drug (when available) describing how to take the drug.

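### The GH risk text names m-cresol as the allergen while the preparation sections describe a benzyl alcohol diluent, and no listed criterion excludes known hypersensitivity to GH or its diluent

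*Combined protocol and SAP*

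**What the plan says.** Section 11.0, under subcutaneous GH administration, lists uncommon but potentially severe effects. One is "allergic reactions to a chemical called *m*-cresol, which is part of the study drug injection". No other component of the injection is named there as an allergen.

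The preparation sections are specific about what is injected. Section 6.4.6.1 says that 5.8 mg vials will be used and that the powder is "reconstituted with bacteriostatic water (contains benzyl alcohol as a preservative". Section 6.4.6.3 repeats that nurses prepare the dose "using a vial of diluent (bacteriostatic water with benzyl alcohol". Section 6.4.6.2 fits this, with one storage rule for the powder and another for the mixed product: "the reconstituted form that is used for injection will be stored for 3 weeks then discarded".

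On eligibility, section 3.1 has 13 items and section 3.2 has 16. The broadest exclusion, item 16, imports "Other Exclusion Criteria proposed by the World Health Organization COC Contraindications", a list concerned with oral contraceptives. Two removal criteria in section 3.3.1 come near the point. Item 4 is "Identification of a disease or underlying health condition that precludes participation in the study" and item 6 is "Subject does not respond well to contraceptive therapy or GH administration, potentially compromising her health".

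**The concern.** A risk paragraph should describe the product that participants receive. Here it attributes the allergy risk to a component that the preparation sections do not mention, and it leaves out the one preservative that they do. If consent wording was drawn from section 11.0, a volunteer who knows that she reacts to benzyl alcohol would not be alerted, and one who reacts to m-cresol might be deterred without cause.

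The eligibility lists do not close the gap. Keeping out a woman with a known allergy to GH or its diluent would depend on clinical judgement under general rules, not on a written criterion. The volunteers are healthy and receive GH as a physiological probe, not as treatment, so even a small avoidable risk deserves a line in the criteria.

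**Working it through.** The plan states no figure on this point, so there is none to reproduce. The check is a comparison of sections and a count.

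**Step 1. What the injection contains, by section.**

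| Section | GH presentation | Component named |
|---|---|---|
| 6.4.6.1 Receipt | 5.8 mg powder vials, reconstituted | benzyl alcohol (diluent preservative) |
| 6.4.6.2 Storage | powder and reconstituted forms | none |
| 6.4.6.3 Preparation | powder vial plus vial of diluent | benzyl alcohol |
| 11.0 Risks | not stated | m-cresol (allergen) |
| 3.3.2 Withdrawn subjects | pen and cartridges | none |

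Benzyl alcohol appears nowhere in section 11.0, and m-cresol appears nowhere in section 6.4. Section 3.3.2 refers to a pen and cartridges, which does not match vials. Text written for another presentation may have been left in place, but that is an inference. No section gives the full ingredients of the vial.

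**Step 2. Eligibility items.** 13 inclusion + 16 exclusion = 29 items. Items naming hypersensitivity to GH, its diluent or any excipient: 0 of 29. No visible item names allergy to the pill, patch or ring either; the external list behind exclusion item 16 is not available.

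**Step 3. Who receives GH.** Section 6.1 has the control group complete every procedure except contraceptive therapy, so all four groups are dosed. Section 6.4.2 gives 8 dosing days per woman, 4 at baseline and 4 post-study. Planned completers are 4 × 12 = 48. This shows only that the point applies to every group. The documents give no allergy rate, so no expected number of reactions follows.

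**Step 4. Existing safeguards.**

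- Before dosing: the medical history questionnaire and physical exam (section 6.2.1), prescription by a study clinician (section 6.4.6.3), and removal item 4. The exam is described as covering general health and contraindications to hormonal contraception.
- At dosing: "The injections will be given by the CRC nursing staff", and administration follows the manufacturer's instructions for use (section 6.4.6.1).
- Information: drug leaflets are handed out when available (section 6.4.6.3).
- After dosing: removal item 6, and routine questioning about how participants feel (section 20.2).

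None of these, as written in the protocol, names benzyl alcohol or requires a woman with a known GH or diluent allergy to be kept out before the first dose.

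**The case against.** The strongest reply is that the documents show a difference in naming and little more. They nowhere state that benzyl alcohol is an allergen or that hypersensitivity is a contraindication. They do not list the vial's ingredients. The list of potentially severe effects is not presented as complete, and it already alerts readers to allergy to an injected component. The phone screens, the medical history form, the consent form and the manufacturer's sheets are not in the documents, and any of them may ask about allergy. Exclusion items 2, 10 and 12 (metabolic or endocrine, liver or renal, and thyroid conditions) bear on other GH risks. Clinicians are on site (section 16.4) and a medical monitor is named (section 21.1.1). Women with a known GH allergy are probably few, because known endocrine disease is excluded.

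Most of this stands, and it limits the point. It does not remove it. The protocol itself treats a component of the injection as a possible allergen, so naming the component that its own preparation sections specify is a matter of internal consistency. An exclusion for a known allergy to a product about to be injected needs no incidence figure to justify it.

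Three stronger readings are tempting and are not supported:

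- **That the m-cresol warning is false.** Without an ingredient list this cannot be shown.
- **That GH is held to a laxer allergy standard than the contraceptives.** No visible criterion names a pill, patch or ring allergy either.
- **That the number of women dosed measures harm.** It counts exposure only.

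**Conclusion.** The concern holds as a minor safety and consent-consistency correction. Section 11.0 names one allergen, and it is not the one preservative that section 6.4.6 says is injected. None of the 29 listed criteria excludes known hypersensitivity to GH or its diluent, although every group receives GH.

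The finding is about the protocol text. A reader might infer that participants are misinformed or go unscreened for allergy. The documents do not establish that, because the forms that would settle it are not available. The size of any clinical effect is unknown. Endpoints, sample size and analysis are unaffected.

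The conclusion assumes that the vial presentation in sections 6.4.6.1 to 6.4.6.3 is the one in use. If a pen and cartridges are used instead, those sections need the correction, and the risk text should be checked against that product. The missing exclusion remains either way.

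**What to change.** 1. Confirm which Omnitrope presentation is used, and its ingredients.
2. In section 11.0, and in any consent text drawn from it, name the preservative actually injected. If vials are confirmed, that is benzyl alcohol in the diluent. Remove m-cresol unless it is a confirmed ingredient.
3. Add an item 17 to section 3.2, for example: *Known hypersensitivity to somatropin or to the preservative in its diluent.* Check it on the existing screening medical history form.
4. As a clerical matter, if vials are confirmed, delete the pen and cartridges from section 3.3.2.

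The cost is a few lines of text and one question on a form already in use. The downside is an occasional excluded volunteer.
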